Study Procedure	
Once rolled over to compassionate use study, patients will visit the study center every 3 months until documented disease progression or treatment discontinuation due to toxicity or consent withdrawal. During these visits, Tenalisib will be dispensed and medication compliance will be monitored. In case of roll over from a combination study, the investigator has a choice to continue with the combination therapy or to maintain the patient on Tenalisib monotherapy. If combination agent is continued, it will be administered as a part of SOC.
 
Safety and efficacy assessments will be done as mentioned below.
 
• Safety assessments: Safety assessments will be done during these visits and AEs will be reported as required by the protocol. There are no specific safety labs or evaluations (including vitals, physical examinations, pregnancy tests and ECGs) required as per protocol. As part of SOC, laboratory tests or other evaluations will be done per Investigator's discretion. Adverse events (AEs, SAEs and deaths) will be recorded and reported until 30 calendar days after last dose or until a new anti-cancer treatment is initiated, whichever is earlier. After this period, only AEs, SAEs, or deaths assessed by the investigator as treatment related are to be reported.• Efficacy assessments: Disease assessments should be performed as part of SOC. Date of disease progression will be recorded in the CRF.• Drug dispensing: Patients will be given drug supply of 3 months.
Estimated Study duration	Approximately 5 years
Assessment of Response	Efficacy evaluations will be performed as per physician's discretion as part of SOC. These evaluations (e.g. measurement of lymph node, mSWAT) will not be recorded in CRF, however the date of disease progression will be reported.
Study Treatment	Patients showing clinical benefit will continue to receive Tenalisib as they are currently receiving in previous protocols. The treatment plan will be the same dosing schedule unless dose adjustments or delays are necessary for toxicity management. In case of roll over from a combination study, the investigator has a choice to continue with the combination therapy or to maintain the patient on Tenalisib monotherapy. If combination agent is continued, it will be administered as a part of SOC.

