5.3 Prohibited Medications

The following treatments are prohibited while on the compassionate study protocol:

- Any other anti-lymphoma therapy (e.g. radiation therapy, hormonal therapy for cancer,

cancer immunotherapy or other biologic therapy).

- Herbal medications are not allowed throughout the trial. Patients should stop using these herbal medications at least 7 days prior to C1D1.
- **Strong inhibitors or inducers of CYP3A4** including grapefruit products, herbal medication. Patients should stop using these medications at least 7 days prior to C1D1.
- **Strong inhibitors or inducers of CYP2C9** including herbal medications. Patients should stop using these medications at least 7 days prior to C1D1.
- **Substrates of CYP3A4 enzyme with a narrow therapeutic range** (e.g. Warfarin and phenytoin). Patients should stop using these medications at least 7 days prior to C1D1.
- Steroids > 20 mg unless for management of toxicity.

Discontinuation of patient who received concomitant/prohibited medication will be taken by the PI in consultation with medical monitor on case by case basis, after reviewing ongoing clinical benefit and risk. The decision to allow a patient to continue will be documented.

5.4 Procedures for Monitoring Subject Compliance.

The following measures will be employed to ensure treatment compliance. Subjects will be asked to bring any unused study drug to the study center at their next visit. Site personnel will count and record the number of used and unused study drug tablets at each visit. The study coordinator will question the patient regarding adherence to the dosing regimen, record the number of tablets and strengths returned, the date returned and determine treatment compliance before dispensing new medication to patient.

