6.3 Treatment and Study Procedures

Patients will visit the study center every three months until documented disease progression or treatment discontinuation due to toxicity or consent withdrawal. During these visits, Tenalisib will be dispensed and medication compliance will be monitored. Safety and efficacy assessments will be done as mentioned below.

- Safety assessments:**

- Safety assessment will be done during the visits and AEs will be reported as required by the protocol.
- Concomitant medications may be administered as clinically indicated.
- A medication history should be reviewed at each clinic visit to assure no potential adverse events are noted.
- There are no specific safety labs or evaluations (including vitals, physical examinations, pregnancy tests and ECGs) required as per protocol. As part of SOC, laboratory tests or other evaluations can be done per Investigator's discretion. Adverse events (AEs, SAEs and deaths) will be recorded and reported for 30 calendar days after last dose or until a new anti-cancer treatment is initiated, whichever is earlier. After this period, only AEs, SAEs, or deaths assessed by the investigator as treatment related are to be reported.

- Efficacy assessments:**

- Disease assessments [e.g. radiological imaging (e.g. CT, PET-CT) or any other appropriate evaluation tool (e.g. mSWAT in case of skin involvement)] should be performed as part of SOC. These evaluations (e.g. measurement of lymph node, mSWAT) will not be recorded in the CRF, however, date of disease progression will be reported .

- Drug dispensing:**

- Patients will be given drug supply for 3 months.

Table 1: Schedule of Events

	Screening and Eligibility	Cycle 1	Cycle 4	Cycle 7 Through EOT	EOT	EOS ¹¹
Day	D-14 to D1	D1	D1	D1	-	-
Window period	-14	-	±7	±7	-	+30
Study Days	D-14 to D1	1 ¹	85	169	-	-
Informed Consent	X	-	-	-	-	-
Eligibility Confirmation	X	-	-	-	-	-
Demographics ²	X	-	-	-	-	-
Medical history ³	X	-	-	-	-	-
Vitals	-	SOC*	SOC*	SOC*	SOC*	-
Weight ⁴	X	SOC*	SOC*	SOC*	SOC*	-
Physical exam	-	SOC*	SOC*	SOC*	SOC*	-
ECOG Performance	X	SOC*	SOC*	SOC*	SOC*	-
Complete blood count	-	SOC*	SOC*	SOC*	SOC*	-
Chemistry	-	SOC*	SOC*	SOC*	SOC*	-
PT/INR	-	SOC*	SOC*	SOC*	SOC*	-
Urinalysis (routine)	-	SOC*	SOC*	SOC*	SOC*	-
Pregnancy test ⁴	-	SOC*	SOC*	SOC*	SOC*	-
12-lead ECGs	-	SOC*	SOC*	SOC*	SOC*	-
Disease assessment ⁵	-	SOC*	SOC*	SOC*	SOC*	-
Date of discontinuation ⁶	-	-	-	-	X	-
Drug Dispensing ⁷	-	X	X	X	-	-
Tenalisib treatment ⁸	-	X	X	X	-	-

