9. All AEs should be recorded spanning from the informed consent drug until 30 calendar days after the last dose of study drug or till new anti-cancer treatment is initiated whichever is earlier.
10. All events that meet the definition of serious but, in the opinion of the treating investigator, are clearly expected from the Patient's disease or related to disease progression (i.e. there exists no reasonable possibility that they were caused by the study drug) should be reported on the case report forms and do not require expedited reporting. In addition, progression of malignancy (including fatal outcomes), if documented by use of appropriate method (e.g. CT/ PET) or clinically confirmed, should not be reported as a serious adverse event.
11. Patients should be followed for AEs for 30 calendar days after the last dose of study treatment or till new anti-cancer treatment is initiated whichever is earlier. Telephonic follow up during this period is acceptable. All new AEs occurring during this period should be reported and followed until resolution unless, in the opinion of the investigator, the adverse event or laboratory abnormality/ies are not likely to improve because of the underlying disease.

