7.2 Adverse Event/Serious Adverse Event Causality Assessment

The causality assessment will be categorized as related and not related.

- **Related:** All toxicities should be considered to be related to Tenalisib unless there is a clear alternative explanation.
- **Not related:** If there is no temporal association, or another etiology has been identified as the cause, or the trial treatment cannot be implicated based upon the current information.

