3 ASSESSMENT OF EFFICACY

3.1 Adverse Events

Any untoward medical occurrence in a patient or clinical investigation subject administered a pharmaceutical product and which does not necessarily have a causal relationship with this treatment.

All adverse events should be graded as per the CTCAE v5.0. and should be recorded in the case report form. All adverse events resulting in discontinuation from the trial should be followed until resolution or stabilization. Patients must be followed for AEs for 30 calendar days after the last dose of study treatment or till new anti-cancer treatment is initiated whichever is earlier. All new AEs occurring during this period must be reported and followed until resolution unless, in the opinion of the investigator, the adverse event or laboratory abnormality/ies are not likely to improve because of the underlying disease. After 30 days of completion of protocol-specific treatment or discontinuation, only AEs, SAEs, or deaths assessed by the investigator as treatment related are to be reported.

The causality assessment will be categorized as related and not related.

- **Related:** All toxicities should be considered to be related to Tenalisib unless there is a clear alternative explanation.
- **Not related:** If there is no temporal association, or another etiology has been identified as the cause, or the trial treatment cannot be implicated based upon the current information.

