3.3 Protocol-Defined Events of Special Interest

The following are events of special interest and will need to be reported expeditiously.

- Pregnancy, Abortion, Birth Defects/Congenital Anomalies

Congenital anomalies/birth defects always meet SAE criteria, and should therefore be expeditiously reported as an SAE, using the previously described process for SAE reporting. A Pregnancy Form should also have been previously completed and will need to be updated to reflect the outcome of the pregnancy.

- Overdose

An overdose is defined as accidental or intentional administration of any dose of product that is considered both excessive and medically important. For purposes of this trial, an overdose will be defined as any dose exceeding the proposed dose of Tenalisib (e.g. > 800 mg twice a day).

The safety endpoints will include:

- Incidence of AEs and related AEs
- Incidence of grade 3, grade 4 and grade 5 AEs
- Incidence of SAEs and deaths

The analyses of safety will be based on the frequency of adverse events for patients who received at least one dose of study treatment.

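### Full AE recording can end at a new anti-cancer treatment while Tenalisib continues, so non-serious AEs judged unrelated go unrecorded; the SAE reporting windows also conflict

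*Combined protocol and SAP*

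**What the plan says.** **When full AE recording ends.** Protocol Table 1, footnote 9, runs AE recording from informed consent "until 30 calendar days after the last dose of study drug or till new anti-cancer treatment is initiated whichever is earlier". Section 6.3 has the same two limbs, the second being the start of such treatment, with the earlier date governing: "Adverse events (AEs, SAEs and deaths) will be recorded and reported for 30 calendar days after last dose or until a new anti-cancer treatment is". The synopsis (Study Procedure) gives the same rule. Both then add: "After this period, only AEs, SAEs, or deaths assessed by the investigator as treatment related are to be reported".

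**What may happen on treatment.** Section 5.3 prohibits other anti-lymphoma therapy, with radiation as one example. It leaves discontinuation of a patient who received a prohibited medication to the investigator and medical monitor, case by case: "The decision to allow a patient to continue will be documented".

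**What other sections say about the window.** Section 7.3.2 requires the sponsor to be told of every SAE, whatever its causality, from consent through 30 days after the last dose. It has no new-treatment limb. Section 7.1.2 and SAP 3.1 start the related-only period at another point: "After 30 days of completion of protocol-specific treatment or discontinuation, only AEs, SAEs, or deaths assessed by the investigator as treatment related".

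**How the data are used.** SAP 3.3 lists the incidence of all AEs, related AEs, grade 3, 4 and 5 AEs, SAEs and deaths. The analysis set is everyone dosed: "The analyses of safety will be based on the frequency of adverse events for patients who received at least one dose of study treatment".

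**The concern.** A rule that stops AE collection at a new anti-cancer treatment makes sense once the study drug has ended, because later events are hard to attribute. Footnote 9 is not limited to that situation. It defines the whole recording period from consent, so for a patient who is given added therapy and kept on Tenalisib, the earlier date falls during treatment.

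Safety is the first study objective, and SAP 3.3 summarises simple frequencies with no censoring or exposure adjustment. A patient whose recording has been cut short stays in the denominator and appears free of any later event that was not collected.

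The loss may also be selective. Section 7.2 makes an event not related where "another etiology has been identified as the cause, or the trial treatment cannot be implicated based upon the current information", and an added therapy readily supplies another etiology. Events arising while the two treatments overlap are therefore among those more likely to be classed as unrelated and left out.

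**Working it through.** The documents give no event rate, no frequency of prohibited therapy and no sample-size calculation, so there is no plan figure to reproduce. The check is a comparison of the texts followed by a simple bound.

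**Step 1: can the cut-off fall on treatment?** Footnote 9, the synopsis and 6.3 take the earlier of two dates and do not tie the second to the end of Tenalisib. Section 5.3 prohibits other anti-lymphoma therapy but does not make discontinuation automatic. If such therapy starts on day T and Tenalisib continues to a later day L, the earlier of T and L + 30 is T, which precedes L. On the literal text the answer is yes.

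**Step 2: what is still collected between T and L?**

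| Event after T, Tenalisib ongoing | Synopsis and 6.3 | 7.3.2 | 7.1.2 and SAP 3.1 |
|---|---|---|---|
| Related, non-serious | Reported | Not applicable | No explicit rule |
| Unrelated, non-serious (any grade) | Not reported | Not applicable | No explicit rule |
| Related SAE or death | Reported | Reported | No explicit rule |
| Unrelated SAE or death | Not reported | Reported | No explicit rule |

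The last column has no explicit rule because general follow-up there can end at T, while the related-only period starts only 30 days after completion or discontinuation. Deaths from documented progression are kept out of SAE reporting by 7.3.1 and are not part of this point.

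The second row is lost under footnote 9, the synopsis and 6.3. The fourth row depends on which section a site follows. Related events are retained, and 7.2 makes related the default: "All toxicities should be considered to be related to Tenalisib unless there is a clear alternative explanation".

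**Step 3: effect on an incidence in SAP 3.3.**

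- N = about 50 (synopsis, number of patients).
- k = patients given new anti-cancer therapy and kept on Tenalisib. The documents do not give this; it is assumed.
- m = those among the k whose first event in a given AE category comes after T and is not recorded, so m ≤ k.
- x = patients who truly have an event in that category.

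True incidence is x/N and recorded incidence is (x − m)/N. The shortfall is m/N, which is at most k/N.

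| Assumed k | Maximum shortfall k/50 |
|---|---|
| 1 | 1/50 = 2 percentage points |
| 2 | 2/50 = 4 percentage points |
| 5 | 5/50 = 10 percentage points |

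The maximum is reached only if every one of the k patients has a first event of that category after T that is non-serious and judged unrelated. The related-AE incidence is not reduced under 6.3, and the SAE incidence is not reduced where 7.3.2 is followed.

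**The case against.** The strongest reply is that the clause was meant only to shorten the 30-day tail after the last dose. Several places fit that reading. Table 1 marks AE and SAE evaluation at every visit through EOT, with no exception for added therapy, and EOT is the day of the last dose. Footnote 11 and section 6.5 use the clause for end-of-study follow-up. Sections 7.1.2 and SAP 3.1 date the related-only period from completion or discontinuation. Footnote 3 has medically significant history at later visits captured as an AE.

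The route is also narrow. It needs a protocol-prohibited therapy and a documented decision to continue. The case-by-case sentence in 5.3 covers every listed item, including herbal products and CYP inhibitors, and is not aimed at anti-lymphoma therapy in particular. Progression is itself a listed reason to discontinue. The study is descriptive, with no comparator, so no formal inference rests on these incidences.

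Most of this stands as evidence of intent and of small scale. It does not remove the problem. Footnote 9 is attached to the AE row of Table 1 and starts at consent, so it cannot be read as a rule for the tail alone. The words of 5.3 do reach anti-lymphoma therapy. And the sections that support the benign reading disagree with 6.3 and the synopsis, so two sites could collect different data for identical patients.

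**Conclusion.** The point holds in a limited form. On the literal text, a patient kept on Tenalisib after new anti-cancer therapy has non-serious AEs judged unrelated, including non-serious grade 3/4, left unrecorded while still counting in the SAP 3.3 denominator. All-cause AE incidence can then be biased downward, by at most k/50 for any one category: 2 to 10 percentage points if 1 to 5 patients are affected. That range rests on an assumed k and about 50 patients. Separately, 6.3 and the synopsis conflict with 7.3.2 on SAEs and deaths, and with 7.1.2 and SAP 3.1 on when related-only reporting begins.

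A reader might infer more than this, without support in the documents:

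- *That on-treatment AEs as a whole drop out for these patients.* Related AEs stay reportable under 6.3, and 7.3.2 retains all SAEs.
- *That safety oversight is lost.* Three-monthly visits, one-day SAE notification and medical monitor review of cumulative data all continue.
- *That restarting a combination partner dropped at rollover triggers the cut-off.* Section 5.1 gives the investigator a choice on rollover, no section provides for a later restart, and new anti-cancer treatment is not defined.
- *That a given share of on-drug time is lost per patient.* The documents give no timings from which to calculate one.

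The change is still worth making: it settles a contradiction about what sites must collect for the safety endpoint.

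**What to change.** State once, and repeat consistently, that all AEs and SAEs are recorded throughout Tenalisib treatment whatever other anti-cancer treatment is given. After the last Tenalisib dose, full recording continues for 30 calendar days or to the start of a new anti-cancer treatment, whichever comes first, and only then does related-only reporting begin.

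Align Table 1 footnotes 9 and 11, the synopsis, sections 6.3, 6.5, 7.1.2 and 7.3.2, and SAP 3.1. In 7.3.2, make explicit whether the new-treatment limb shortens the post-dose SAE window, so that it no longer conflicts with 6.3 and the synopsis.

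The cost is an edit to a few sentences and slightly more AE recording at visits that already take place. No dose or clinical rule changes. If recording through the last dose was always intended, the edit only makes that plain.

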6.4 End of Trial Treatment (EOT)

The day of the last dose of study drug will be considered as EOT. Reason of discontinuation should be recorded.

6.5 End of Study (EOS)

All patients will be followed for adverse events until 30 calendar days after the last dose of study drug or until new anti-cancer treatment is initiated whichever is earlier. Telephonic follow up is acceptable. In case of drug related AEs, further safety assessments will be performed as warranted, at the discretion of PI. The patient will be followed until resolution or stabilization of related adverse event.

7 ASSESSMENT OF SAFETY

7.1 Adverse Events

7.1.1 Definitions of adverse events

Any untoward medical occurrence in a patient or clinical investigation subject administered a pharmaceutical product and which does not necessarily have a causal relationship with this treatment.

7.1.2 Recording of adverse events

All adverse events should be graded as per the CTCAE v5.0. and should be recorded in the case report form. All adverse events resulting in discontinuation from the trial should be followed until resolution or stabilization. Patients must be followed for AEs for 30 calendar days after the last dose of study treatment or till new anti-cancer treatment is initiated whichever is earlier. All new AEs occurring during this period must be reported and followed until resolution unless, in the opinion of the investigator, the adverse event or laboratory abnormality/ies are not likely to improve because of the underlying disease. After 30 days of completion of protocol-specific

treatment or discontinuation, only AEs, SAEs, or deaths assessed by the investigator as treatment related are to be reported.

7.2 Adverse Event/Serious Adverse Event Causality Assessment

The causality assessment will be categorized as related and not related.

- **Related:** All toxicities should be considered to be related to Tenalisib unless there is a clear alternative explanation.
- **Not related:** If there is no temporal association, or another etiology has been identified as the cause, or the trial treatment cannot be implicated based upon the current information.

7.3 Serious Adverse Events

7.3.1 Definitions of serious adverse events

An SAE or reaction is defined as any untoward medical occurrence that: results in death, is immediately life-threatening, requires at least a 24-hour in-patient hospitalization or prolongation of existing hospitalization, results in persistent or significant disability/incapacity, is a congenital anomaly/birth defect or an important medical event.

All events that meet the definition of serious but, in the opinion of the treating investigator, are clearly expected from the Patient's disease or related to disease progression (i.e. there exists no reasonable possibility that they were caused by the study drug) should be reported on the case report forms and do not require expedited reporting. In addition, progression of malignancy (including fatal outcomes), if documented by use of appropriate method (e.g. CT/ PET) or clinically confirmed, should not be reported as a serious adverse event.

Treatment within or admission to the following facilities is not considered to meet the criteria of “in-patient hospitalization” (although if any other SAE criteria are met, the event must still be treated as an SAE and immediately reported):

- Emergency Department or Emergency Room
- Outpatient or same-day surgery units
- Observation or short-stay unit
- Rehabilitation facility
- Hospice or skilled nursing facility
- Nursing homes, Custodial care or Respite care facility

Hospitalization during the trial for a pre-planned surgical or medical procedure (one which is planned prior to entry in the trial **or** planned in advance and not related to the study procedure/drug), does not require reporting as a serious adverse event to the Sponsor.

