7.3.2 Serious adverse event reporting by Investigators

Adverse events classified by the treating investigator as **serious** require expeditious handling and reporting to sponsor in order to comply with regulatory requirements. Serious adverse events may occur at any time from the signing of the informed consent form through the 30-day follow-up period after the last dose of study drug. Sponsor/sponsor representative must be notified of all SAEs, regardless of causality, within 1 day of the first knowledge of the event by the investigator. The SAE report should be sent to the sponsor/sponsor representative **via e-mail**. Follow-up

information for SAEs and information on non-serious AEs that become serious should also be reported to Sponsor as soon as it is available. Investigators must report SAEs and follow-up information to their responsible IRB/IEC according to the policies of the responsible IRB/IEC.

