3.2 Serious Adverse Events

- Definitions of serious adverse events

An SAE or reaction is defined as any untoward medical occurrence that: results in death, is immediately life-threatening, requires at least a 24-hour in-patient hospitalization or prolongation of existing hospitalization, results in persistent or significant disability/incapacity, is a congenital anomaly/birth defect or an important medical event.

All events that meet the definition of serious but, in the opinion of the treating investigator, are clearly expected from the Patient's disease or related to disease progression (i.e. there exists no reasonable possibility that they were caused by the study drug) should be reported on the case report forms and do not require expedited reporting. In addition, progression of malignancy (including fatal outcomes), if documented by use of appropriate method (e.g. CT/ PET) or clinically confirmed, should not be reported as a serious adverse event.

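### The planned-procedure exemption in protocol 7.3.1 lets a scheduled admission for a new on-study condition go unreported as an SAE if it is judged unrelated, which conflicts with 7.3.2 for that narrow group

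*Combined protocol and SAP*

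**What the plan says.** Protocol 7.3.1 defines an SAE and includes the usual hospitalization criterion, an in-patient stay of at least 24 hours. It then exempts hospitalization during the trial for a pre-planned surgical or medical procedure and explains pre-planned by two alternatives joined by an emphasised *or*:

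- the procedure is "one which is planned prior to entry in the trial"; or
- it is "planned in advance and not related to the study procedure/drug), does not require reporting as a serious adverse event to the Sponsor".

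Protocol 7.3.2, on reporting by investigators, states: "Sponsor/sponsor representative must be notified of all SAEs, regardless of causality, within 1 day of the first knowledge of the event by the investigator".

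SAP 3.2 repeats the SAE definition, including an event that "requires at least a 24-hour in-patient hospitalization or prolongation of existing hospitalization". It also repeats the paragraph on disease-related events and progression. It does not carry over the planned-procedure exemption. The safety endpoints listed at the end of SAP 3.3 include "Incidence of SAEs and deaths", with no restriction to related events.

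**The concern.** The first ground is ordinary: an admission already booked at entry is not a new safety event. The second ground is different. It does not require that planning came before entry or consent, or that the condition was pre-existing and stable. Apart from being planned, the only test is that the procedure is not related to the study procedure or drug.

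Suppose a patient has a fracture on study and surgery is booked for the following week with an in-patient stay of at least 24 hours. That is an untoward occurrence leading to hospitalization. Judged related, it is reported as an SAE. Judged unrelated, 7.3.1 can be read to waive the report. For this kind of event, membership of an all-cause endpoint then depends on a causality call by the investigator in an open-label study without a comparator.

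The stake is moderate. Safety is the first objective and SAEs are a named endpoint. No laboratory tests or other safety evaluations are required by the protocol, so AE and SAE reports are the main safety data. The estimated duration is about 5 years, long enough for new conditions to lead to scheduled admissions. An admission not reported as an SAE also brings no one-day notice to the sponsor.

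**Working it through.** The plan states no figure on this point, so there is none to reproduce. The check is a comparison of the sections, followed by simple arithmetic on scale.

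**Step 1. What the second ground adds.** A procedure planned before entry is already exempt under the first ground. The second ground has independent effect only if it reaches procedures planned after entry. Its wording allows that, because planning in advance is tied to no date.

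**Step 2. The same admission under each section.** Take a new or worsened on-study condition treated by a scheduled in-patient stay of at least 24 hours.

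| Section | Judged related | Judged unrelated |
|---|---|---|
| Protocol 7.3.1, SAE definition | Meets hospitalization criterion | Meets hospitalization criterion |
| Protocol 7.3.1, planned-procedure exemption | Not exempt | Exempt from SAE reporting |
| Protocol 7.3.2 | Notify | Notify |
| SAP 3.2, SAE definition | Meets criterion | Meets criterion; exemption not mentioned |
| Protocol 7.1.2 | Recorded and graded as an AE | Recorded and graded as an AE |

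The conflict lies in the right-hand column, between the second and third rows.

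**Step 3. Comparison with the other carve-outs in 7.3.1.** The list of facilities that do not count as in-patient hospitalization adds that an event meeting any other SAE criterion must still be handled as an SAE. Serious events attributed to the disease "should be reported on the case report forms and do not require expedited reporting". The planned-procedure exemption carries neither safeguard.

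**Step 4. Scale.** Inputs: N = 50, from the protocol synopsis (approximate; section 9 gives no formal sample size), assuming all are treated and so enter the safety analysis; k = number of patients whose only SAE is an exempted admission, which the documents do not give.

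Shift in SAE incidence = k / N.

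- k = 0: 0/50 = 0 points
- k = 1: 1/50 = 2 points
- k = 2: 2/50 = 4 points
- k = 3: 3/50 = 6 points
- k = 5: 5/50 = 10 points

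The range of k from 0 to 5 is an assumption to show scale. A patient with another reported SAE does not change the incidence.

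**The case against.** The strongest reply is that the sections can be read in sequence. Section 7.3.1 stands under a heading on definitions and settles what counts; 7.3.2 then governs events the investigator has classified as serious, and its all-causality rule applies to those. A natural target of the second ground is an elective procedure with no untoward event behind it, which is not an SAE in any case. For a real new event, the investigator could still call the condition serious on another criterion, such as an important medical event.

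Part of this stands. The wording is ambiguous, and there is no conflict for purely elective admissions. But the sentence does not say that the event is not serious; it says that it need not be reported as an SAE. That is a reporting waiver, and it meets the reporting rule in 7.3.2 head on. Relying on an investigator to find another criterion does not settle what the plan requires.

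Other limits stand in full:

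- Unplanned unrelated admissions remain reportable, and the first ground has no relatedness test.
- Protocol 7.2 presumes relatedness unless there is a clear alternative explanation, which shrinks the exempt group.
- The underlying event stays in the CRF as an AE, and so in the AE and grade 3 to 5 summaries.
- No formal sample size or decision rule depends on the SAE rate.

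A reader might infer that the protocol also contradicts SAP 3.2. The documents do not support that. SAP 3.2 states no causality-independent rule. It has its own judgement-based provision for disease-related events and says that documented or clinically confirmed progression "should not be reported as a serious adverse event". It leaves out the planned-procedure sentence, as it leaves out the facility list. That is an omission to repair, not a contradiction.

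**Conclusion.** The point holds for a narrow subset: scheduled in-patient stays of at least 24 hours for a condition that arises or worsens on study and is judged unrelated. For these, 7.3.1 waives a report that 7.3.2 requires, and the all-cause SAE incidence in SAP 3.3 can be understated. What is lost is the SAE label and the prompt notice to the sponsor, not the AE record.

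The size is 2 percentage points for each patient whose only SAE is exempted, given about 50 treated patients. The number of such patients is unknown and may be zero, so no expected bias can be stated.

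A reader might go further and conclude that SAE incidence as a whole depends on causality, or that the related share among SAEs is materially inflated. Neither is supported. Most routes to an SAE involve no relatedness test, the documents give no inputs for a related share, and that share is not among the listed endpoints. The correction is worth making because it is specific and cheap, and because SAEs are a named endpoint.

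**What to change.** Put 7.3.1, 7.3.2 and SAP 3.2 under one rule:

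- In 7.3.1, limit the exemption to (a) admissions planned before informed consent for a condition that has not worsened since, and (b) elective admissions with no new or worsened medical condition behind them. Remove relatedness as a ground.
- In 7.3.2, leave the all-causality rule as it is and refer to the revised exemption, so that sites see the two together.
- In SAP 3.2, repeat the revised sentence so that the events counted in the analysis match those that sites are told to report.

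The cost is one sentence in the protocol with a cross-reference, the same sentence in the SAP, and a few more SAE forms. The change concerns reporting only and leaves treatment and visits untouched.
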